9.3.3 DCCV group

Sedation maintained for 30 minutes. An electrophysiological catheter will be passed to the superior vena cava using fluoroscopic guidance and 6 minutes of phrenic pacing will be performed, starting at 20 minutes following first local anaesthetic. At 30 mins, sedation optimised and DCCV performed. Sheath withdrawal, Femostop haemostasis and protamine as per local protocol. An implantable loop recorder will be inserted in the prepectoral area with local anaesthetic at the end of the procedure.

9.3.4 All patients

Recovered to ward. 12 lead ECG performed but not shown to patient. Patient mobilised and discharged after 4 hours.

Blinding

There is a study specific Standard Operating Procedure on the blinding procedure used in this study. No information on the procedure given will be transferred from cath lab staff to the recovery ward staff.

Patients and other healthcare professionals will also be blinded to which treatment the patient received. The cath lab staff performing the procedure will have no further contact with the patient during the study. A 'chaperone' will be assigned for each patient, who will take over from the cath lab staff in caring for the patient post intervention.

A standard procedure report will be used for clinical records, with a procedure report entered into the study database. This will be transferred to the clinical database at the end of the study or at a patient unblinding event, whichever is earlier.

In the present study we will use a modification of the blinding procedure used in the ORBITA trial (Al-Lamee et al., 2018). A specific blinding questionnaire will be used at the end of the day of the intervention asking the patient and ward staff to guess the treatment allocation. As is typical of AF studies involving ablation, a blanking period will be observed. This accounts for the frequent recurrence of arrhythmia in the days following ablation, where healing atrial tissue can be vulnerable to arrhythmia which is not predictive of longer-term outcome. At the end of the blanking period (ie. 6 weeks) patients will be asked to complete the blinding questionnaire again. This blinding index will be reported on the day of the intervention and at 6 weeks and 3 months follow up to allow the degree of blinding to be assessed.

[figure not shown]
9.4 Schedule of Assessment

Assessment	Screening/ pre-admission	Randomisation	Treatment/ Procedure	Implant	Recovery	6 weeks (telephone)	3 month (clinic)	12 month /EOS (clinic)	Monthly downloads	Registry
Visit window							+/- 7 days	+/- 2 weeks		
Informed consent	X									
Patient baseline characteristics recorded: estimated AF duration, LA dimensions (echo), LVEF, Bloods, Medications, Age, Sex, BP, CHADS VASC score, co-morbidities, demographics, weight, height, BMI.	X									
Randomisation		X								
DCCV only			X							
DCCV plus Pulmonary Vein Isolation			X							
Telephone FU						X				
Quality of life measures	X					X	X			
Clinical FU						X	X	X		
Loop recorder inserted				X						
12 lead ECG					X		X	X		
Interrogation of loop recorder				X			X	X	X	
Symptom questionnaires	X					X	X	X		
Clinical status and mortality data										X

The long term passive follow up will track patient mortality and clinical status from routinely collected clinical data. No intervention or investigations will be performed as part of this long term follow up.

9.5

Study Scheme Diagram

9.6 Blinding procedures

The aim of blinding will be to prevent patients, their treating clinicians and their treatment choices being influenced by knowledge of the procedure being performed. The pilot study will establish the effectiveness and feasibility of blinding procedures. Patients will be admitted to the day ward for "Orbita AF DCCV±ablation". They will undergo confirmation of study and procedural consent by a senior cardiology fellow/registrar or consultant. Patients will be accompanied to the cath lab by a clinical fellow or research nurse (Chaperone), and at this point their care will be transferred to the cath lab team. The patient will enter the catheter lab and standard AF preprocedural checks will be performed. Patients will be offered to wear headphones playing relaxing music of their choice during the procedure. A groin access / draping pack will be opened for all patients and sedation given. After GCS < 10, the patient will be randomised to either DCCV and ablation, or DCCV alone using REDcap (mobile app). The procedure will be performed according to protocol. At the end of the procedure, a "sign out" will be performed, where the procedure performed is confirmed to the operating team. Here the randomised allocation will not be specified in keeping with the blinding SOP. If no complications occurred, the procedure performed will not be specified on sign-out, hand over to the ward staff will be as follows:

"A DC cardioversion plus or minus Cryoablation under the study protocol was performed with groin sheath access and no complications. The patient should be managed assuming they have undergone an ablation procedure".

Patients who are accidentally unblinded will be withdrawn from the trial.

Patients will complete a questionnaire immediately prior to discharge to establish their perception of which procedure was performed.

Randomisation will be performed in a 1:1 ratio, between 3 and 4 patients per day will have procedures performed as per this protocol. Individual randomisation will be performed after insertion of groin sheath and administration of sedation.

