9.7 Follow up

Patients will be followed up for a total of 12 months regardless of the results of any interim analysis. Monthly remote interrogation of the loop recorder will measure the burden of AF (proportion of time in AF) and the duration of AF episodes. At follow up patients will undergo interrogation of their loop recorder, a 12 lead ECG and a symptom questionnaire. For patients travelling long distances for their treatment ECGs and device interrogations will be requested from their local device centre and questionnaires will be administered by telephone, mail and or email. Patients will remain within an observational registry for 5 years following the end of the trial.

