9.10 Subject Withdrawal

Patients can withdraw from the trial at any time and without giving a reason. The Principal Investigator can also withdraw a patient from the study for any of the following reasons:

1. Any adverse event or serious adverse event
2. Any concurrent illness that prevents further treatment
3. Any change in the patient's condition that justifies the discontinuation of treatment in the clinician's opinion
4. Withdrawal of consent for treatment by the patient
5. Any study device or procedural complications
6. Any reasons the subject cannot adhere to study visits or procedures

If a patient withdraws from the study, another patient will be randomised to replace them. Patients who are randomised but withdraw will not have their medical care affected and return to standard clinical care.

10. Assessment and management of risk

The risks of both DC cardioversion and of catheter ablation for AF are well established, as detailed below. However, the procedures will be performed by experienced clinicians who part of the research team for all study participants, which should minimise any known/expected risks.

10.1.1 DCCV risks:

- Sedation complications (<1%), chest discomfort, redness, irritation at site of skin pads (5%), failure of DCCV.

10.1.2 Catheter ablation of AF risks:

- Groin access complications (1% historically, <0.2% with ultrasound guidance)
- Minor (Total <6%)
 - Groin: Bleeding bruising at groin access site (5%)
 - Pericardial effusion not requiring drainage (1%)
 - Transient phrenic nerve palsy (3%)
- Major (Total <1%)
 - Groin complication or vascular damage requiring surgical or radiological intervention (0.5%)
 - Cardiac tamponade requiring percutaneous drainage (0.7%)
 - Stroke (<0.2%)
 - Oesophageal damage (<0.2%)
 - Death (<0.1%)
 - Pulmonary vein stenosis causing breathlessness (<0.1%)

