11.2 Method of analysis

The statistical analysis plan (SAP) will describe the statistical methods which will be used in the analysis of data, including any interim analyses and the level of significance that is to be used.

Progression criteria

This study has been designed with an internal pilot phase aimed at assessing the feasibility and optimizing the methods to be used in the main study, piloting key study logistics, improving quality and efficient use of resources. Eldridge (Eldridge et al., 2016) have described a new framework where 'internal pilot' studies which have some feasibility objectives but focus on the processes to be used in the main study generating data which can contribute to the final analyses. They describe the use of operational 'progression criteria' which can be used to measure pre-identified targets at the end of the pilot phase which will determine whether or not to proceed to the main trial. This approach has been advocated by the members of the Internal Pilot Trials Workshop supported by the Hubs for Trials Methodology Research (Avery et al., 2017). Avery and colleagues describe some of the key issues to consider in development and review of these criteria.

In the current study the following progression criteria have been identified to assess operational aspects of the design and progression to the main trial:

- Protocol non-adherence – (a) cross-over from DCCV to AF ablation group. Estimate 25-30% as in CABANA trial (Packer et al., 2018). We will take this level of cross-over into account in our power calculations. (b) Measure the amount of off protocol intervention.

- Recruitment rate – we estimate being able to recruit 4 patients per month. If the number falls below this we will need to build this into timelines for the larger trial.
- Loss to follow-up. Estimate 2%.
- Key study logistics – especially around the delivery of the intervention, including the use of a 'chaperone' to maintain blinding.
- Identifying barriers and facilitators to implementation.
- Assessment of the success of the blinding procedure (ie. blinding index).
- Assessment of the feasibility of the blinding SOP.
- Assessment of the acceptability of the interventions
- Data collection – completeness and quality. How much missing data are we willing to tolerate?
- Assessment of outcome measures.

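### Accidentally unblinded patients are withdrawn and nothing says their data collection continues, so known blinding failures can leave the later blinding index and later endpoint data are likely lost

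*Protocol*

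**What the plan says.** Protocol 9.6 gives the rule without qualification: "Patients who are accidentally unblinded will be withdrawn from the trial". The same section gives the pilot a purpose that bears directly on it: "The pilot study will establish the effectiveness and feasibility of blinding procedures".

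Protocol 9.10 covers what follows a withdrawal. "Patients who are randomised but withdraw will not have their medical care affected and return to standard clinical care", and "If a patient withdraws from the study, another patient will be randomised to replace them". Its list of reasons for which the investigator may withdraw a patient does not include unblinding.

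Otherwise, Protocol 9.7 sets full follow-up: "Patients will be followed up for a total of 12 months regardless of the results of any interim analysis". On blinding, the Blinding text under Protocol 9.3.4 states: "This blinding index will be reported on the day of the intervention and at 6 weeks and 3 months follow up". Protocol 11.2 lists the blinding index among the progression criteria.

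SAP 6.4.5 defines the primary endpoint as a proportion of randomised patients, and SAP 7.2.1 analyses everyone randomised in the assigned group. SAP 6.4.4 and 11.3 limit the calculations to complete cases or available data. SAP Table 2 reports the patient index after the procedure, at 6 weeks and at 3 months, and the staff index after the procedure only. It has no row for accidental unblindings.

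**The concern.** The rule selects on the quantity that the pilot is meant to measure. A patient known to have learned the allocation is a known blinding failure. If that patient leaves before a later questionnaire, the reported index describes only patients in whom blinding was not known to have failed. The replacement patient brings a new guess and does not restore the lost failure.

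The second cost is endpoint data. The intervention is one procedure on day 0, so there is no continuing trial treatment to stop, and withdrawal afterwards most naturally means the end of trial follow-up. An intention-to-treat label cannot bring back visits and recordings that were never collected. The registry does not clearly recover them either: Protocol section 8 and SAP 7.1.1 describe registry follow-up for patients who complete the 12-month visit and consent.

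Under SAP 6.1, pilot patients join the main trial if it is judged feasible and the design has no major change. Gaps in their 12-month data could not be filled then.

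**Working it through.** **Which readings are affected.** Assume that withdrawal ends data collection.

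| Time of accidental unblinding | Patient index readings missing | Other data missing |
|---|---|---|
| Before the discharge questionnaire | possibly all three | later visits and recordings |
| After discharge, before 6 weeks | 6 weeks and 3 months | later visits and recordings |
| Between 6 weeks and 3 months | 3 months | later visits and recordings |
| After 3 months | none | rest of the 12 months |

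The staff index is taken only after the procedure, so later unblinding does not touch it.

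**Inputs.** 10 patients per arm (Protocol section 4) and the Bang index on its −1 to 1 scale (SAP 6.4.4). The plan gives no expected number of accidental unblindings and no index cut-off, so there is no figure of its own to reproduce. Two assumptions are added: 1 to 3 of 10 patients in an arm are unblinded, and each would answer correctly if asked.

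**Formula.** Index for an arm = (correct − incorrect)/N. Let u be the fraction unblinded and b the index in the rest.

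- Everyone kept: u + (1 − u)b.
- Unblinded removed: b.
- Fall: u + (1 − u)b − b = u(1 − b). This is positive when b < 1 and zero when b = 1.
- Standard error with everyone kept: √[(p_correct + p_incorrect − index²)/N].

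**Results, N = 10.**

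| Unblinded | Rest: right/wrong/don't know | Index, all kept | Index, removed | Fall | SE, all kept |
|---|---|---|---|---|---|
| 1 | 4/4/1 | (5−4)/10 = 0.10 | 0/9 = 0 | 0.10 | 0.298 |
| 2 | 4/4/0 | (6−4)/10 = 0.20 | 0/8 = 0 | 0.20 | 0.310 |
| 3 | 3/3/1 | (6−3)/10 = 0.30 | 0/7 = 0 | 0.30 | 0.285 |
| 2 | 5/3/0 | (7−3)/10 = 0.40 | 2/8 = 0.25 | 0.15 | 0.290 |
| 2 | 3/5/0 | (5−5)/10 = 0 | −2/8 = −0.25 | 0.25 | 0.316 |
| 3 | 3/4/0 | (6−4)/10 = 0.20 | −1/7 = −0.14 | 0.34 | 0.310 |

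The falls run from about 0.3 standard errors (0.10/0.298) to about 1.1 (0.34/0.310). When the rest guess evenly or better, blinding looks better than it was. When b is negative the result varies: the fifth row moves away from 0, while the sixth crosses 0 and ends closer to it.

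**If rule and index carry over to the main trial.** At 104 per arm the standard errors in the first three rows shrink by √(10/104) = 0.310, to about 0.09 to 0.10. The fall u(1 − b) does not depend on N, so it stays at 0.10 to 0.30.

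**The case against.** The strongest reply is that data loss is inferred. The documents do not define withdrawal. Protocol 12.4 says that the investigator will comply if a withdrawing subject asks for follow-up results not to be entered, which could imply that they are entered otherwise. Protocol 17.3 runs adverse-event reporting to the 12-month visit and makes no exception for withdrawn patients. This stands as far as it goes: a reader might infer that all later data are certainly lost, and the documents do not establish that. They leave the matter open, with loss as the natural reading.

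Reporting is not blank either. SAP section 8 plans completion of each study phase by arm in the Consort structure, so these patients would show as not completing. Some might also surface in the off-protocol deviation row of Table 2, the deviation log (Protocol 17.8) or the qualitative review of the blinding SOP. The flow diagram and that SOP are not visible here. What remains is that no visible output names unblinding as the reason.

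The index measures guesses, and a patient who has been told is no longer guessing. An index without such patients is defensible if they are counted separately, which is a reason to report both.

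Finally, no decision is shown to change. The pilot has no hypothesis test (SAP 6.5) and no index cut-off, and the Trial Steering Committee judges progression by discussion. It is tempting to add that one withdrawal is 1/20 = 5%, above the 2% loss to follow-up estimated in Protocol 11.2. But 2% of 20 is 0.4 of a patient, so any single loss for any reason exceeds it; the 2% is an estimate, not a threshold; and the SAP does not say that these withdrawals count as lost. That comparison carries no weight here.

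**Conclusion.** The concern holds in a limited form and should be fixed. The withdrawal rule, the replacement rule and available-data analysis together can remove known blinding failures from the 6-week and 3-month patient index. They also sit badly with an analysis of all randomised patients.

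Under the stated assumptions, with the rest guessing evenly, an arm's index falls from 0.10–0.30 to 0. This is about one standard error or less, so it would not be distinguishable from chance in the pilot. The case rests on the selection being built in by rule, avoidable at low cost, and inherited by the main trial if the rule stays.

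Two stronger readings are not supported. One is that the rule always makes blinding look better: the index does not move at b = 1, and when b is negative it can end nearer to 0 or further from it. The other is that the SAP itself excludes these patients: it does not, and the difficulty is that the protocol rule may leave it without their data.

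**What to change.** - **Protocol 9.6:** replace the withdrawal sentence. Accidentally unblinded patients stay in follow-up (visits, questionnaires, loop-recorder downloads) and in the intention-to-treat set unless they withdraw consent, and the date and reason of unblinding are recorded.
- **Protocol 9.10:** align it, stating that accidental unblinding does not by itself end data collection.
- **SAP 6.4.4:** state that unblinding alone is not loss to follow-up.
- **SAP Table 2:** add a row counting accidental unblindings by arm, and report the 6-week and 3-month patient index with and without these patients.

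The cost is a short protocol amendment with ethics committee review, and revised patient information and consent forms if they describe withdrawal. A few unblinded patients would remain in follow-up. Their later symptom and quality-of-life answers should be flagged, since knowledge of the allocation could affect them; the primary endpoint, read from the loop recorder, is less exposed.

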9.7 Follow up

Patients will be followed up for a total of 12 months regardless of the results of any interim analysis. Monthly remote interrogation of the loop recorder will measure the burden of AF (proportion of time in AF) and the duration of AF episodes. At follow up patients will undergo interrogation of their loop recorder, a 12 lead ECG and a symptom questionnaire. For patients travelling long distances for their treatment ECGs and device interrogations will be requested from their local device centre and questionnaires will be administered by telephone, mail and or email. Patients will remain within an observational registry for 5 years following the end of the trial.

9.8 End of Study Definition

The last patient attending for the 12 month clinic assessment will mark the end of the study. Patients who have consented to have their AF data collected will then go into the registry for 5 years. Once all the data has been collected from the last clinic assessments then final data analysis will be completed.

9.9 Entry into Registry

Following study completion, patients will be entered into a data registry which will gather standard clinical data from patient notes. This will follow patients up for 5 years.

9.10 Subject Withdrawal

Patients can withdraw from the trial at any time and without giving a reason. The Principal Investigator can also withdraw a patient from the study for any of the following reasons:

1. Any adverse event or serious adverse event
2. Any concurrent illness that prevents further treatment
3. Any change in the patient's condition that justifies the discontinuation of treatment in the clinician's opinion
4. Withdrawal of consent for treatment by the patient
5. Any study device or procedural complications
6. Any reasons the subject cannot adhere to study visits or procedures

If a patient withdraws from the study, another patient will be randomised to replace them. Patients who are randomised but withdraw will not have their medical care affected and return to standard clinical care.

10. Assessment and management of risk

The risks of both DC cardioversion and of catheter ablation for AF are well established, as detailed below. However, the procedures will be performed by experienced clinicians who part of the research team for all study participants, which should minimise any known/expected risks.

10.1.1 DCCV risks:

- Sedation complications (<1%), chest discomfort, redness, irritation at site of skin pads (5%), failure of DCCV.

10.1.2 Catheter ablation of AF risks:

- Groin access complications (1% historically, <0.2% with ultrasound guidance)
- Minor (Total <6%)
 - Groin: Bleeding bruising at groin access site (5%)
 - Pericardial effusion not requiring drainage (1%)
 - Transient phrenic nerve palsy (3%)
- Major (Total <1%)
 - Groin complication or vascular damage requiring surgical or radiological intervention (0.5%)
 - Cardiac tamponade requiring percutaneous drainage (0.7%)
 - Stroke (<0.2%)
 - Oesophageal damage (<0.2%)
 - Death (<0.1%)
 - Pulmonary vein stenosis causing breathlessness (<0.1%)

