7.2 Exclusion criteria

Patients who meet the following exclusion criteria will be ineligible for study participation;

- Creatinine clearance (eGFR) < 30mls/min
- Contraindication or unable to take anticoagulation
- Contraindication or unable to tolerate amiodarone
- Uncontrolled hypertension
- Contraindication or catheter ablation
- BMI > 35

8. Study design

Barts Health patients referred from other Barts Health NHS Trust Hospitals (Homerton, Chase Farm, Barnet) for either cardioversion for persistent AF or catheter ablation of persistent AF will be approached for recruitment.

- All patients:
 - Patient drug treatment will follow local clinical guidelines for AF ablation and be recorded in the CRF.
 - Patient baseline characteristics recorded at preadmission
 - Estimated AF duration
 - LA dimensions (Echocardiogram)
 - Ejection fraction
 - Routine Bloods

- Creatinine & Electrolytes,
- Full blood count,
- Thyroid function
- Quality of Life measures
- BP
- CHADS VASC score / assessment
- Medical History and Comorbidities
- Demographics (Age, sex, ethnicity)
- Physical exam (BP, HR, Weight, Height, BMI)
- Medications
- Day of Procedure – blinded randomisation to intervention (DCCV, or Pulmonary Vein Isolation plus DCCV). Reveal LINQ inserted during procedure.
- 6 weeks: QoL measures, telephone FU
- 3 months: Clinical follow up, 12 lead ECG, Repeat QOL measures
- 12 months: Clinical follow up, Endpoints measured. Once subject participation in the trial is complete, the patient and physician will be unblinded. If the patient is in AF, management of AF proceeds as clinically indicated.
- All patients who consent to have data capture continue in AF registry for 5 years.

The pilot study patients will be analysed at 3 months and 12 months to allow assessment of feasibility of a larger trial, and patients who complete the 12 month follow-up visit and consent will continue in registry follow-up for 5 years post procedure.

9. Study procedures

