17.3 Notification and reporting of Adverse Events and Reactions

If the AE is not defined as serious, the AE will be recorded in the study documents and the participant followed up by the research team. The AE will be documented in the participants' source documents, the Case Report Form (CRF), and, where appropriate, medical records.

The following events will be considered and reported as Adverse Events, and not serious adverse events, as they are expected as known complications of procedures:

- Phrenic nerve damage
- Tamponade or pericardial effusion
- Haematoma
- Skin Burns
- Chest pain
- Groin vascular complications.

The period for adverse events reporting will be from the signing of consent until the end of study visit at 12 month follow-up.

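### Protocol 9.10 permits investigator withdrawal and replacement of a randomised patient for any adverse event or procedural complication, and no text keeps that patient's data collection going to 12 months

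*Protocol*

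**What the plan says.** Protocol 9.10 opens its list with "The Principal Investigator can also withdraw a patient from the study for any of the following reasons". Reason 1 is "Any adverse event or serious adverse event" and reason 5 is "Any study device or procedural complications". Neither carries a threshold for severity, relatedness or timing. The section continues: "If a patient withdraws from the study, another patient will be randomised to replace them", and "Patients who are randomised but withdraw will not have their medical care affected and return to standard clinical care".

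Protocol 17.3 states: "The period for adverse events reporting will be from the signing of consent until the end of study visit at 12 month follow-up". For a non-serious event it adds that "the AE will be recorded in the study documents and the participant followed up by the research team". It does not mention withdrawn patients, and 9.10 does not refer to it.

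On the registry, Protocol section 8 says that "patients who complete the 12 month follow-up visit and consent will continue in registry follow-up for 5 years post procedure". Protocol 9.9 is worded more broadly and does not repeat that condition.

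The SAP defines the intention-to-treat set as everyone randomised, by assigned group (7.2.1), and the safety set as those randomised who received the allocated treatment (7.2.2). Analysis uses patients with endpoint data (11.3). There is no rule for withdrawn or replaced patients.

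**The concern.** In a drug trial, withdrawal for an adverse event usually means stopping the drug. Here the intervention is a single session, and the synopsis gives treatment as one day. Once it is over, little or no trial treatment is left to stop, so withdrawing the patient from the study mainly ends observation, and harm is the stated ground for ending it.

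At stake are the resolution or persistence of the complication, any later death, admission or repeat procedure, and the 12-month recurrence, ejection fraction and quality-of-life results in that patient. Several of these are listed endpoints (Protocol 6.4; SAP 6.4.5). If patients leave because they were harmed, their missing outcomes are unlikely to be missing at random. SAP 6.1 allows pilot patients to be carried into the main trial, so any selection would go with them.

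**Working it through.** **1. The passages side by side**

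| Question | Text | Answer |
|---|---|---|
| Withdrawn from what? | Protocol 9.10 | The study, not only treatment |
| Required or permitted? | Protocol 9.10 | Permitted, at the investigator's discretion |
| What follows? | Protocol 9.10 | Ordinary care, plus a newly randomised replacement |
| Do adverse event data continue? | Protocol 17.3 | The window runs to 12 months; withdrawn patients are not addressed |
| Do visits, downloads or vital status continue? | No passage | Not stated |
| Is the registry a fallback? | Protocol 8 and 9.9 | Section 8 ties entry to completing the 12-month visit; 9.9 is broader |
| How are missing outcomes treated? | SAP 6.4.4, 11.3 | Complete cases, available data |

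The SAP's primary endpoint is a 12-month proportion (6.4.5) with no rule for partial follow-up. A patient withdrawn early without a recorded recurrence would either drop out of the analysis or be counted as recurrence-free. Table 5 counts patients with an event within a year over N, so a patient removed early but kept in N would be treated as fully observed.

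**2. The denominator**

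The main-trial size reproduces. The hazard ratio is ln(1 − 0.66)/ln(1 − 0.47) = 1.699. Freedman's formula at 80% power and 5% (two-sided assumed) gives 117 events, and 117/0.565 = 207.1, so 104 per group. That figure is not in dispute. It is used below with the pilot's 10 per group.

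**3. How many could qualify**

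Inputs are the rates in Protocol 10.1.2. Upper bounds are taken as rates, and items as non-overlapping.

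- *Ablation-specific items.* Effusion 1, phrenic palsy 3, tamponade 0.7, stroke 0.2, oesophageal damage 0.2, death 0.1, vein stenosis 0.1: sum 5.3%.
- *Stated totals.* Minor below 6 and major below 1: up to 7%.
- *All minor and major items.* Minor 5 + 1 + 3 = 9; major 0.5 + 0.7 + 0.2 + 0.2 + 0.1 + 0.1 = 1.8: sum 10.8%. This leaves out the separate groin-access line above the two lists.

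The items add to more than the stated totals (9 against 6; 1.8 against 1), so all three bases are shown. The chance of at least one among 10 is 1 − (1 − p)^10.

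| Basis | p | At least one of 10 | Expected of 104 |
|---|---|---|---|
| Ablation-specific | 5.3% | 1 − 0.947^10 = 42% | 5.5 |
| Stated totals | 7% | 1 − 0.93^10 = 52% | 7.3 |
| All listed items | 10.8% | 1 − 0.892^10 = 68% | 11.2 |

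For comparison, the planned 2% loss to follow-up (Protocol 11.2) is 0.2 of 10 and 2.1 of 104. Reason 1 reaches further than this table, since it covers any adverse event, but the documents give no overall adverse event rate.

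**The case against.** The strongest reply is that 17.3 already covers the point: its window runs from consent to the 12-month visit with no exception, and its text has the research team follow up a participant with a non-serious event. That reading is available. But 17.3 does not say that it applies after withdrawal, and 9.10 sends the patient to ordinary care. Two reasonable sites could act differently.

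A reader might also draw four stronger conclusions, which the documents do not support.

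- *Safety follow-up necessarily stops.* Section 9.10 says the investigator can withdraw, not must, and no passage says collection then ceases. Protocol 9.7 adds no contradiction: its 12-month commitment concerns interim analysis results, not withdrawal.
- *The harm disappears.* The triggering event should be recorded under 17.3 and appear in the SAP's complication, bleeding, adverse event and serious adverse event outputs. The patient stays in the intention-to-treat set. Loss to follow-up is reported by arm over all randomised (SAP 6.4.4 and Table 2), and the safety committee sees unblinded data.
- *An uncomplicated patient takes the place.* A replacement takes the next allocation on an unstratified list (SAP 7.4), may enter either arm and runs the risks of the arm assigned. No text excludes the patient who was withdrawn.
- *The rule bites at about 10.8% under ablation against about 6% under cardioversion.* That contrast passes over the stated totals. It also ignores shared exposure: both arms have sedation, femoral sheaths and heparin, and the ablation arm is cardioverted if still in AF. The 5.5% of groin items (5% + 0.5%) therefore cannot be charged to ablation alone. The 5.3% is the part treated here as specific to ablation.

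It also stands that reason 1 can operate before randomisation, since consent and event reporting begin at pre-admission. Withdrawal then costs no randomised data. And if the loop recorder itself fails, its downloads cannot continue.

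**Conclusion.** The concern holds as a defect in wording that permits loss of follow-up in harmed patients. The permission to withdraw for any adverse event or complication, and the replacement, are explicit. That observation can then end early is an inference from three facts: treatment lasts one day, the patient goes to ordinary care, and no text continues data collection.

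The exposure is to later events and 12-month outcomes, not to the first event. Between 5.3% and 10.8% of ablation patients could qualify through a listed ablation complication, depending on which of the protocol's own figures is used, against a planned 2% loss. This rests on upper bounds used as rates and on items not overlapping. It says nothing about how often the investigator would use the permission, so it is not an estimate of bias.

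The pilot makes no hypothesis tests (SAP 6.5), which limits the consequence now. The wording should still be corrected, because follow-up of harmed patients should not rest on discretion and the pilot data may enter the main trial.

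**What to change.** For randomised patients, reword Protocol 9.10 as follows.

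- An adverse event or complication may end further study procedures, but is not by itself a ground for ending follow-up.
- Adverse event, vital-status and visit data, and loop-recorder data where the device works, continue to 12 months unless the patient withdraws consent for data collection.
- These patients stay in the intention-to-treat analysis and in safety reporting, and are not replaced because of an adverse event or complication.

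Add a cross-reference so that 9.10 and 17.3 agree, and a sentence in the SAP on how withdrawn and any replaced patients are handled. Withdrawal before randomisation can stay as it is. The change concerns data collection only and leaves clinical decisions where they are.

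The cost is wording. The visits and downloads are already in the schedule of assessments. The downside is that the pilot may end with slightly fewer uncomplicated completers.
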